#### 10.2.6 Reporting Events to Participants

Study participants will be informed about AEs and SAEs where that information may be relevant to their participation in the study or during their participation in the study, such as correct operation of ambulatory equipment.

#### 10.2.7 Unanticipated Problems

##### A. Unanticipated Adverse Device Effect (UADE)

An Unanticipated Adverse Device Effect (UADE) is defined as any serious adverse effect on health or safety or any life-threatening problem or death caused by or associated with the study device if that effect, problem or death is not previously identified in nature, severity or degree of incidence in this investigational plan or application, or any other unanticipated serious problem associated with a device that relates to the rights, safety or welfare of subjects.

In the event of a UADE, the research site staff will notify the IRB/EC as soon as possible. A written report will be provided to the IRB/EC within their reporting guidelines.

##### B. Reporting Unanticipated Problems to Participants

Study participants will be informed about Unanticipated Problems where that information may be relevant to their participation in the study or during their participation in the study, such as the correct operation of ambulatory equipment.

### 11 Supporting documentation and operational considerations

#### 11.1 Study oversight and integrity

The Investigator/Sponsor is committed to ensuring that the data are generated, documented and reported in compliance with ICH-GCP, the protocol and the applicable regulatory requirements.

#### 11.2 Institutional Review Board (IRB)

The Investigator will seek IRB approval before the final protocol is implemented.

#### 11.3 Protection of Human Subject (Informed Consent/Process)

Patients will be required to sign an Informed Consent prior to performing any study specific activity.

To obtain Informed Consent in compliance with the Regulations (21 CFR § 812 and § 50, 45 CFR Part 46, 21 CFR Part 50, 21 CFR Part 56 and ICH-GCP) each patient must be fully informed about the investigation, including:

- An explanation of the study procedure;
- The potential risks and/or discomforts;
- The potential benefits;
- Information regarding whom to contact for answers about the study and their rights as a research participant;
- An explanation that participation is voluntary and they can withdraw from the study at any time without prejudice.

Informed Consent shall be provided to the patient in a language that they can read and understand. The Informed Consent forms must include the elements of Informed Consent as required by 21 CFR § 50, Protection of Human Subjects and must be approved by the reviewing IRB.

After the information contained in the Informed Consent documents has been reviewed with each patient, the patient must sign and date the document, indicating willingness to be screened or participate in the clinical study. The investigator or study personnel designated to administrate Informed Consent must sign and date the form. A copy of the signed Informed Consent documents will be given to the patient. The signed Consents should be kept in the hospital/clinic patient file; a copy of the signed consent forms should be placed in the study e-file.

Subjects will be informed if new information becomes available in the course of the study, which may influence a subject's willingness to participate in the study.

The site Principal Investigator is responsible for ensuring proper consenting procedures are followed in this study. The responsibility for performing the consent process may be delegated by the site Principal Investigator to site staff who should have received study training.

The site may use of electronic systems and processes that may employ multiple electronic media to obtain informed consent FDA's requirements for electronic records/electronic signatures, informed consent, and IRBs as set forth in 21 CFR parts 11, 50, and 56, respectively.

#### 11.4 Study Discontinuation and Closure

This study may be prematurely terminated if there is sufficient reasonable cause. If the study is prematurely terminated, the Investigator PI will promptly inform study participants, and the Institutional Review Board (IRB), and will provide the reason(s) for the termination. Study participants will be contacted, as applicable, and be informed of changes to the study visit schedule.

Circumstances that may warrant termination include, but are not limited to:

- Determination of unexpected, significant, or unacceptable risk to participants
- Demonstration of efficacy that would warrant stopping
- Insufficient compliance with protocol requirements
- Data that are not sufficiently complete or evaluable
- The determination that the primary endpoint has been met
- Determination of futility
- An enrollment rate far below expectation that prejudices the conclusion of the study

The study may be discontinued at any time by the IRB as part of their duties to ensure that research participants are protected.

#### 11.5 Confidentiality and Privacy

Participant confidentiality and privacy are strictly held in trust by the Investigator and the clinical research staff. This confidentiality includes the results of any clinical testing and the clinical information relating to participants. Therefore, the study protocol, documentation, data, and all other information generated will be held in strict confidence.

Confidentiality of subject data will be maintained at all times, and any subject information needs

to be de-identified by the participating institution. All documentation relating to a subject will be kept in a secure location.

The site will ensure that the study outcome will not contain any patient identifying data other than the subject ID, which is a unique identifier that links a study subject to his or her medical records at the participating study site. Information will not be released without the written permission of the participant, except as necessary for monitoring by the IRBs, or other regulatory agencies.

All research activities will be conducted in as private a setting as possible.

The study participant's contact information will be securely stored at the site for internal use during the study. At the end of the study, all records will continue to be kept in a secure location for as long a period as dictated by the reviewing IRB, Institutional policies and requirements.

This is a paperless study. The study data entry and study management systems used by the site's research staff will be secured, and password protected within the study EDC system. At the end of the study, all study databases will be de-identified and archived.

#### 11.6 Safety Oversight

This is an early feasibility study designed to gather initial information assessing the changes in LPP and UPP during acute PNS utilizing commercially released, market approved devices. Both the UDT system (Laborie, Sweden) and the implantable neurostimulator (Medtronic, USA;) have been approved by the FDA for their respective indications. The study does not include any invasive nor experimental interventions/treatment. The participating subjects already received the IPG per indication and the urodynamic test is a well-established, verified and institutional standard of care study/test to evaluate the urine storage and release cycle.

Furthermore, the participating sites will have sufficient expertise in managing clinical studies in general and urodynamic testing in particular. The chosen PIs will be qualified investigators who specialize in implanting urology neurostimulators and with adequate study training.

Therefore, there is no Clinical Event Committee (CEC) nor Data Safety Monitoring Board (DSMB) for this study. Yet, an internal safety team comprised of the Investigator and the clinical trial manager will evaluate safety data as soon as the event is reported. All safety information will be collected, analyzed and reported for all eligible subjects who complete UDT during acute PNS cycle.

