### 10.1 General Approach

In this study, only subjects that receive PNS will be included in the analysis. Study subjects that receive acute PNS and complete the UDT will be assessed for safety and evaluation of the changes in LPP and UPP with and without PNS. Study subjects that receive acute PNS and do not complete the UDT will be included in safety analysis only. Study subjects that do not receive acute PNS will be excluded from the study analysis.

Data analysis will comprise of descriptive statistics (means, standard deviations, correlations, etc.) on the outcome measures and variables listed in **Error! Reference source not found.** below.

The final report will include summary data and descriptive statistics of measurements performed in the study, including all Adverse Events and complications reported during the urodynamic test.

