## 10.2 Safety Analyses

All subjects that received acute PNS will be included in the safety analysis. The rate of serious study related adverse events will be summarized as the number of events, the number of subjects with event and the percent of subjects with event within the safety population. There are no formal statistical hypothesis tests. Additionally, the number of all study related AE, the number of subjects with study related AE and the percent of subjects with AE will be summarized by type of event, severity, seriousness and relationship to the study.

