### 10.2.1 Adverse Events (AE)

An Adverse Event (AE) is defined as any untoward medical occurrence in a study subject whether or not considered related to the study device, study procedures or study requirements that is identified or worsens during the study.

Adverse events must be assessed and documented by the investigator at the time of the study procedure visit.

The Investigator should institute appropriate therapeutic and follow-up measures in accordance with good medical practice and record them in the subject's medical history.

All AEs will be captured on the appropriate CRF. Information to be collected includes event description, time of onset, clinician's assessment of severity, relationship to study procedure (assessed only by those with the training and authority to make an assessment), and time of

resolution/stabilization of the event.

Any medical condition that is present at the time that the participant is screened will be considered as baseline and not reported as an AE. However, if the study participant's condition deteriorates at any time during the procedure visit, it will be recorded as an AE.

A list of possible risks associated with the study procedure are included in the section titled "Known potential risks" within this document.

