#### 10.2.5 Time Period and Frequency for Event Assessment and Follow-Up

The occurrence of (S)AE may come to the attention of study personnel during study visits, or upon review by a study monitor. All AEs occurring during the study must be documented appropriately regardless of relationship.

The Principal Investigator will record all reportable events with start dates occurring during the acute stimulation visit. All study related AEs will be followed until 7 days after the end of the study.

All SAEs, and UADEs will be followed until the event is resolved or until a final outcome is established by the Principal Investigator, or for no more than 30 days post the end of the study, whichever occurs first.

Device Deficiencies or Complaints related to any of the market released medical devices utilized during the study or during the clinically indicated procedure should follow standard reporting procedures applicable to device user facilities.

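### Section 11.6 limits safety reporting to eligible subjects who complete the urodynamic test, against 10.1 and 10.2; 10.1 also leaves subjects exposed without stimulation out of the AE summaries and drops non-completers' LPP data

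*Combined protocol and SAP*

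**What the plan says.** Three sections of the combined protocol and SAP determine who is counted for safety.

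- Section 10.2 (Safety Analyses): "All subjects that received acute PNS will be included in the safety analysis". It summarises "the number of all study related AE, the number of subjects with study related AE" and the corresponding percentages. Its rate of serious study-related AEs is expressed as a percentage of the safety population.
- Section 10.1 (General Approach) agrees on PNS recipients who stop early: "Study subjects that receive acute PNS and do not complete the UDT will be included in safety analysis only". It then adds: "Study subjects that do not receive acute PNS will be excluded from the study analysis".
- Section 11.6 (Safety Oversight) closes with: "All safety information will be collected, analyzed and reported for all eligible subjects who complete UDT during acute PNS cycle".

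On recording, 10.2.1 says "All AEs will be captured on the appropriate CRF" and 10.2.5 says "All AEs occurring during the study must be documented appropriately regardless of relationship". Section 10.1 says the final report will give summary data, "including all Adverse Events and complications reported during the urodynamic test".

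Primary endpoint 1 (5.2) is the identification of every study-related AE; primary endpoint 2 is the change in LPP with PNS against without. Enrolment is at most 15 (6.1). Section 10 plans no hypothesis test and no power calculation.

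**The concern.** The safety sentence in 11.6 cannot hold together with 10.1 and 10.2 for a PNS recipient who does not complete the UDT. The direction matters. Section 9.5 names an AE as a reason for withdrawal, so conditioning on completion removes the subjects most likely to have had an event. The eligibility condition narrows the set further: 9.5 foresees subjects found to meet an exclusion criterion that had not been recognised before, and such a subject may already have been exposed. Section 9.4 keeps the data of consented subjects who fail eligibility out of the analysis.

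The second gap lies in 10.1 itself. The antibiotic and equipment set-up (7.1) come before stimulation (7.2), UDT and antibiotic risks are listed in 8.1.1 and 8.1.2, and 9.5 names inability to receive PNS as a withdrawal reason. An AE in such a subject falls outside the 10.2 summaries, although primary endpoint 1 is meant to cover all study-related AEs.

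The third gap concerns primary endpoint 2. Section 7.3 collects OFF and ON assessments at successive bladder volumes, yet 10.1 uses none of them if the subject is judged not to have completed the UDT.

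**Working it through.** The plan gives no non-completion rate, AE rate or precision target, so it has no figure to reproduce. The check compares the definitions and then illustrates them with assumed counts.

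**Who is counted**

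| Subject | 10.1 / 10.2 safety | 11.6 safety | 10.1 LPP analysis |
|---|---|---|---|
| PNS, UDT completed, eligible | in | in | in |
| PNS, UDT not completed | in | out | out |
| PNS, UDT completed, later found ineligible | in under 10.2; 9.4 may remove | out | in under 10.1; 9.4 may remove |
| Antibiotic or UDT set-up, no PNS | out | out | out |

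The definitions disagree on the second and third rows. The fourth row is missing from both safety sets.

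**What completion means.** No definition is given. Step 7.3.8 ends LPP testing at several named points, including discomfort and any reason of the investigator. Section 8.1.3 lists temporary discomfort as a stimulation risk expected in more than 10%. The same stop can therefore be a planned test end and an AE. Section 9.5, on replacement, speaks of the UDT having been completed both with and without PNS, but 7.3.6 allows the ON step to be omitted when there is no leak OFF or at the physician's discretion.

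**Illustration A: AE stops after PNS.** Assume 15 PNS recipients (the upper limit in 6.1), no replacement, and AEs only in those who stop. Let k be the number who stop with an AE and j the number of these classed as completers.

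- Rate under 10.2 = k/15
- Rate under 11.6 = j/(15 − k + j)

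For k = 2, with Clopper-Pearson 95% intervals:

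| Rule | Count | Rate | 95% CI |
|---|---|---|---|
| 10.2 | 2/15 | 13.3% | 1.7 to 40.5 |
| 11.6, j = 0 | 0/13 | 0% | 0 to 24.7 |
| 11.6, j = 1 | 1/14 | 7.1% | 0.2 to 33.9 |
| 11.6, j = 2 | 2/15 | 13.3% | 1.7 to 40.5 |

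**Illustration B: AE before any PNS.** Assume 15 subjects start Visit 2 procedures, one has an antibiotic or catheter AE and stops before PNS, and there is no other AE. All exposed: 1/15 = 6.7% (0.2 to 31.9). Under 10.1/10.2: 0/14 = 0% (0 to 23.2).

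**Illustration C: both.** Of 15 who start, one stops before PNS and two after it, each with an AE. All exposed: 3/15 = 20.0%. Under 10.2: 2/14 = 14.3%. Under 11.6, if neither late stopper is a completer: 0/12 = 0%.

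One subject is worth 1/15, or 6.7 percentage points.

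**The case against.** The best defence is that 10.2 is the operative rule. It sits in the Data Analysis section and names the safety population, and 10.1 expressly keeps non-completers in. The 11.6 sentence closes an oversight section explaining why there is no DSMB; it does not use the term safety population, state a denominator or say that only completers count. This stands in part. An analyst would probably follow 10.2, and 11.6 does not formally define a second denominator. But it speaks of collection, analysis and reporting alike and names a different group, so it needs correcting.

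A second defence is that nothing is lost, because all AEs go on CRFs and into the final report. The first half is right, and a reader should not infer that events would go unrecorded. The final-report sentence, however, names events reported during the UDT, does not name those first reported at the follow-up call, and sets no denominator.

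Third, many stops under 7.3.8 read naturally as the planned end of the test. A subject who reached one after an ON assessment would be a completer, and 10.2 and 11.6 would agree. This stands, and it is why the illustration runs down to no gap. Real ambiguity remains where the ON step was omitted or the test was abandoned sooner.

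A reader might also infer that antibiotic AEs cannot reach the study-related tables, because the relatedness question in 10.2.4 mentions only the UDT and PNS. The documents do not support that. Section 10.2.1 points to the known-risks section as the list of study-procedure risks, and that section includes the antibiotic (8.1.2). One limb of the Related category needs only a temporal relationship with the study procedure.

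**Conclusion.** The concern holds in this form. Section 11.6 contradicts 10.1 and 10.2 on who is in the safety analysis. Section 10.1 leaves subjects exposed to the antibiotic or UDT set-up without PNS out of the AE summaries. It also discards usable LPP data from PNS recipients who do not complete the UDT. What is at risk is the 10.2 counts and denominator for primary endpoint 1 and the data used for primary endpoint 2; AE capture is not at risk.

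The size cannot be fixed from the documents. With the assumed 2 AE stops among 15 recipients, 11.6 understates the 10.2 rate by between 0 and 13.3 percentage points. The upper end needs both stoppers to be classed as non-completers and should not be read as the expected effect. The group exposed without PNS is probably small, because amplitude titration (7.2) precedes bladder filling (7.3), so most subjects who begin LPP testing will already have had PNS. The study is descriptive, so no test or error rate is affected. The change should still be made before analysis: these rates are the planned safety summary, and section 10 says the results may be used to design a powered study.

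**What to change.** 1. **One safety population in 10.1, 10.2 and 11.6:** every subject who starts Visit 2 study procedures (antibiotic given or any UDT catheter placed), with PNS recipients shown as a subset. Delete the eligibility and completer conditions from 11.6. State in 9.4 that a subject already exposed stays in safety even if later found ineligible, and in 9.5 that replaced subjects stay in safety.
2. **LPP change in 10.1:** include every subject with at least one paired OFF/ON assessment, whether or not the test ran to its end. An OFF-only subject contributes no change, so give these as a separate count or listing with the reason ON was not tested.
3. **Completion:** define it once, for replacement under 9.5 and for reporting the number and reasons of early stops. After items 1 and 2, neither analysis set depends on it.

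Optional clarification only: name the antibiotic in the relatedness question of 10.2.4.

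The cost is wording and small table changes, with no new visit, procedure or subject. The reported AE rate may look slightly less favourable.

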#### 11.7 Study Forms

Case Report Forms (CRF) will be used to collect study data. CRFs must accurately reflect the data on the patient's chart and the patient's experience.

The electronic records, such as the CRFs and study regulatory documents, will be encrypted and secured with password protection. The database will only contain de-identified subject information. Electronic communication with outside collaborators will involve only unidentifiable information.

All subject related data should be entered and e-signed and dated by the investigator. Every attempt should be made to obtain requested information. However, if a question does not apply, enter N/A (Not Applicable) in the Comment Section. Corrections are tracked by the system and the reason for the change should be given to any change to the data.

#### 11.8 Protocol Deviations

A protocol deviation is any noncompliance with the clinical trial protocol, ICH GCP, or site's SOP requirements.

The investigator will indicate whenever a requirement of the protocol has not been met, using the Protocol Deviation CRF. It is the responsibility of the Investigator to use continuous vigilance to identify and report deviations. All protocol deviation will be reported to the IRB within 5 working days of the deviation.

Protocol Deviations may include but are not limited to:

- Failure to obtain informed consent
- Deviation of the informed consent process
- Not meeting inclusion/exclusion criteria
- Missing required data

All deviations must be reported. The site investigator is responsible for knowing and adhering to their IRB protocol deviations reporting requirements.

#### 11.9 Publication and Data Sharing Policy

This study is designed to gather and report clinically relevant information for the advancement of patient care. It is intended that peer-reviewed publications/abstracts will be generated to report the primary study results.

Study results will be in aggregate form only. Patient's identity will not be publicly disclosed.

## 12 Abbreviations

The list below includes abbreviations utilized in this protocol:

AE	Adverse Event
CFR	Code of Federal Regulations
CMP	Clinical Monitoring Plan
COC	Certificate of Confidentiality
CRF	Case Report Form
EC	Ethics Committee
FDA	Food and Drug Administration
GCP	Good Clinical Practice
HIPAA	Health Insurance Portability and Accountability Act
IB	Investigator's Brochure
ICH	International Conference on Harmonization
IC	Interstitial Cystitis
IRB	Institutional Review Board
ISO	International Organization for Standardization
ITT	Intention-To-Treat
MUI	Mixed Urinary Incontinence
NCT	National Clinical Trial
NIH	National Institutes of Health
OHRP	Office for Human Research Protections
PI	Principal Investigator
QA	Quality Assurance
QC	Quality Control
SAP	Statistical Analysis Plan
SOP	Standard Operating Procedure
SUI	Stress Urinary Incontinence
US	United States
UUI	Urge Urinary Incontinence

